1 BACKGROUND

Research Hypothesis:

Administration of prophylactic apixaban, orally or via a nasogastric or gastric tube (NGT, GT), during induction chemotherapy will reduce the risk of venous thromboembolism (symptomatic + asymptomatic), compared to no systemic anticoagulant prophylaxis, during induction chemotherapy in children with newly diagnosed ALL or lymphoblastic lymphoma (T or B cell) treated with asparaginase.

Schedule of Analyses:

The final analyses for the study will be performed after all subjects either complete the study treatment period followed by a 6-day follow up period, or discontinue prematurely.

2 STUDY DESCRIPTION

Children and adolescents aged 1-18 years with newly diagnosed ALL or lymphoblastic lymphoma (T or B cell) treated with asparaginase will be eligible for this randomized, open-label, study. The subjects on the apixaban arm will receive study drug during approximately 28 days of induction chemotherapy including asparaginase.

2.1 Study Design

The study is designed to compare the effect of prophylactic apixaban versus no administration of systemic prophylactic anticoagulant during planned 3-4 drug systemic induction chemotherapy, on the composite endpoint of adjudicated non-fatal asymptomatic and symptomatic VTE and VTE-related death during approximately 28 days of open-label treatment in subjects (1 to <18 years) with newly diagnosed ALL or lymphoblastic lymphomas (T or B cell), a functioning CVAD and receiving asparaginase during planned 3-4 drug systemic chemotherapy induction.

- There are four study periods extending up to maximum total of approximately five weeks in duration:
- a screening period, between Day -7 to Day 4 \pm 3 days of planned 3-4 drug systemic induction chemotherapy prior to randomization
- a randomization period occurring between Days 1 to 4 \pm 3 of planned 3-4 drug systemic induction chemotherapy
- a treatment period, starting with the day of randomization, and extending through Day 29 \pm 5 days of planned 3-4 drug systemic induction chemotherapy. Subjects \geq 5 years will be administered either 2.5-mg, 0.5-mg tablets or oral solution, use of 2.5-mg or 0.5-mg tablets is encouraged. Subjects <5 years and <35 kg may be administered 0.5 mg tablets only Switching formulations during the course of the study is not encouraged but is allowed.
- a 6 - day (\pm 5 days) follow-up period starting the day after the Day 29 \pm 5 days of 3-4 drug systemic induction chemotherapy

[figure not shown]
Subjects 1 to <18 years of age will be administered apixaban twice daily by mouth or via a NGT or GT according to weight range as per [Figure 2.1-1](#).

Table 2.1-1: Apixaban Doses for Ages 1-18 Years of Age

Weight range	Dose
≥35 kg	2.5 mg twice daily
<35 to 25 kg	2 mg twice daily
<25 to 18 kg	1.5 mg twice daily
<18 to 10.5 kg	1 mg twice daily
<10.5 to 6 kg	0.5 mg twice daily

The study design schematic is presented in Figure 2.1-1.

Figure 2.1-1: CV185155 Study Schematic

2.2 Treatment Assignment

At enrollment, each subject will be assigned a unique sequential number by the Interactive Voice Response System (IVRS). The IVRS will be available 24 hours per day, seven days a week. The subject number will consist of a unique 5 digit number, which is assigned sequentially within a study (starting with 00001) by the IVRS. This number will be used for identification throughout the study and will not be used for any other subject.

Patients will be randomized to apixaban or usual care (no systemic prophylactic anticoagulation) in a 1:1 ratio by the IVRS. Randomization schedules will be generated and kept by Bristol-Myers Squibb. Randomization will be stratified by age groups as < 10 years or ≥ 10 to <18 years, to reflect the major peaks of disease prevalence and risk stratification criteria for acute lymphoblastic leukemia (ALL) in children.

2.4 Protocol Amendments

There were 5 protocol Amendments, and the summaries of major changes for each Amendment are presented in Table 2.4-1 below:

Table 2.4-1: CV185155 Protocol Changes

Document	Date of Issue	Summary of Change
Revised Protocol 05	03-Sep-2020	
Clarified in the study title that it is for ‘Venous’ thromboembolism prevention
 
 Clarified the type of lymphoma subjects permitted in the study 
Added Study Director
 
Redistributed the body weight tier of 9 to < 12 kg into two previous weight tiers to make a 6 to < 10.5 kg weight tier and a 10.5 to <18 kg weight tier
 
Clarified language describing treatment duration
 
Indicated that apixaban oral solution is not to be used in children < 5 years of age
 
[REDACTED]
 
Deleted references to Amendment 3
 
Updated contraception language
 
Added clinically significant bleeding and antiphospholipid syndrome to list of exclusion criteria
 
Clarified that the allowed chemotherapy protocol would be a ‘planned’ 3-4 drug systemic induction
 
Clarified acceptable bilirubin levels
 
Reinforced the collection of radiographic imaging following discontinuation of the study
 
Indicated that PK/PD sampling could occur on days other than Day 7, 8 or 15
 
Clarified the reference GFR values in Appendix 13
 
Updated the Statistical Consideration Sections to be in alignment with the primary analysis population (intent-to-treat or randomized subjects), as well as the sample size calculation included in the Written Request filed with the FDA

Revised Protocol 04	08-Dec-2017	Incorporates Amendment 04
Amendment 04	08-Dec-2017	Changed design of study to indicate that all forms of asparaginase could be used

Table 2.4-1: CV185155 Protocol Changes

Document	Date of Issue	Summary of Change
		
Changed apixaban dosing scheme from a mg/kg dosing to a fixed-dose, body weight-tiered regimen
 
Introduced the 0.5 mg tablet with dosing instructions and development rationale
 
Clarified that the first dose of apixaban should began no later than 12 hours after the first dose of asparaginase
 
Changed enrollment to include children ≥ 1 and < 18 years of age and ≥ 6 kg of weight
 
Indicated that children ≥ 5 years of age can be administered apixaban solution and tablets while children < 5 years of age can only be administered apixaban tablets
 
Indicated that children weighing between 9 and < 12 kg cannot be enrolled in the study until appropriate apixaban formulation/dose available
 
Increased the window of visits from 3 days to 5 days
 
Removed inclusion criteria of having a platelet count $\geq 20,000/\text{microL}$ to administer apixaban and moved to sections regarding apixaban discontinuation and study restrictions and precautions
 
Indicated that Grade 1-2 chemotherapy induced neutropenia or hospitalization for the possibility of neutropenia do not have to be collected as adverse events
 
Move the sensitivity analysis to assess the impact of various primary endpoint event rates in subjects with missing or non-interpretable assessments from the protocol to the Statistical Analysis Plan

Revised Protocol 03	14-Dec-2016	Incorporates Amendment 03
Amendment 03	14-Dec-2016	
The study is only enrolling children > 2 years of age until the dose for children 1 year of age is determined from an ongoing pharmacology study
 
Clarified that the secondary endpoint of CVST included both fatal and non-fatal CVST
 
Added to Secondary endpoints apixaban pharmacokinetics and anti-FXa activity
 

 
Increased the window of when the central venous catheter is inserted to Day -7 to Day 4 of when induction chemotherapy is started
 
Clarified that subjects randomized to apixaban should begin apixaban treatment following randomization and before they start PEG
 
Clarified that if the catheter is to be removed due to the subject experiencing an event other than a VTE or other endpoint related events (eg, bleeding), the subject should not have the study mandated

Table 2.4-1: CV185155 Protocol Changes

[figure not shown]
Document	Date of Issue	Summary of Change
		ultrasound and echocardiogram until Day 29 and should continue with the study treatment
		Allowed subjects to be enrolled who will have the administration of more than one dose of PEG-L asparaginase during the induction chemotherapy
		Allowed subjects to be enrolled who have a mixed-phenotype acute leukemia (MPAL) who will be treated with the COG ALL induction chemotherapy
		Allowed subjects to be enrolled who have had the central venous catheter inserted prior to obtaining informed consent as long as this is part of the subject's standard of care
		Clarified that subjects with a total bilirubin \leq 2XULN can be enrolled
		Clarified that subjects with an INR $>$ 1.4 can't be enrolled
		Removed as an exclusion criteria the PT, PTT, and prolonged Reptilase Time or a prolonged Thrombin Time (TT) values and replaced with an exclusion criteria of an INR $>$ 1.4 and aPTT $>$ 3 seconds above the upper limit of normal for age
		Clarified that the screening period would be between Day -7 to Day 4 of induction chemotherapy
		Allow screening labs to be performed as part of the standard of care prior to signing the informed consent within 1 week prior to enrollment
		Excluded subjects with a risk of bleeding such as hemophilia and von Willebrand disease, etc
		Clarified that the exclusion criteria extreme hyperleukocytosis, white blood cell (WBC) counts over $200 \times 10^9/L$ (200,000/microL) is at the time of enrollment and not at the time of diagnosis
		Clarified that the Doppler ultrasound should be performed for both of the ipsilateral and the contralateral sides whenever possible. If there is difficulty in performing the imaging procedure, the Doppler ultrasound from just the ipsilateral side alone is acceptable
		Indicated that a chest X-ray is not mandated by the study but if one was performed as SOC then it should be submitted as part of the adjudication package
		
		Clarified that decisions to transfuse platelets $>$ 20,000/uL or to interrupt study medication should platelets fall below 20,000/uL is left to the discretion of the clinician

Table 2.4-1: CV185155 Protocol Changes

Document	Date of Issue	Summary of Change
		
Removed surveillance of subject contraception 1 month prior to dosing
 
Clarified that apixaban can be given with or without food 12 hours apart and subjects can take a missed dose up to 6 hours after the normal dosing time
 
Indicated that SAEs need to be collected up to 30 days after the last dose of study medication
 
[REDACTED]

Administrative Letter 02	26-Apr-2016	Specified that labs, exams, and CVD placement as part of standard of care procedures could be used for screening purposes prior to signing the informed consent form
Revised Protocol 02	14-Aug-2015	Incorporates Amendment 02
Amendment 02	14-Aug-2015	
Dose adjustment [REDACTED]
 
The age of subjects eligible for enrollment has been expanded to include children 2 to 18 years of age
 
Clarified the study procedures that should be followed if a catheter is lost or replaced and planned replacements of the catheter is allowed
 
Removed exclusion criteria of Central Nervous Status 3 and replaced with LP's > 3 over the course of the treatment period
 
Clarified the exclusion criteria of 'Major Surgery'
 
Clarified the timing of performing the radiographic imaging
 
Aligned the Secondary safety endpoint and other safety endpoints with the Objectives
 
Added to Exclusion Criteria the administration of any investigational drug including multiple doses of PEG-L asparaginase
 
Added to Prohibited Therapies the chronic daily use of nonsteroidal anti-inflammatory drugs more than 7 days
 
Removed Appendix on "CNS Leukemia at Diagnosis" since exclusion criteria of CNS is being replaced by a number of LP's done during the treatment period, and added a list of NSAIDS.

Administrative Letter 01	04-May-2015	Clarified that the apixaban dose was BID
Revised Protocol 01	28-Jan-2015	Incorporates Amendment 01
Amendment 01	28-Jan-2015	
To align the collection of cerebral spinal fluid to obtain red cell blood counts around the standard of care for the subjects.
 
To clearly define the time period around discontinuing apixaban prior to the lumbar punctures.
 
To clearly define the exclusion criteria of uncontrolled severe hypertension at enrollment using the age, height and gender adjusted standard.

Table 2.4-1: CV185155 Protocol Changes

Document	Date of Issue	Summary of Change
Original Protocol	12-Dec-2014	Not applicable

2.5 Data Monitoring Committee

This study will be conducted under the monitoring of an independent Data Monitoring Committee (DMC), whose activities will be described in a DMC charter. Stopping rules for this study will be developed a priori in collaboration with the DMC. In addition, the DMC will use their clinical and statistical judgment to recommend that the study proceed or be terminated early. This committee is constituted to oversee this apixaban pediatric study.

[figure not shown]
3 OBJECTIVES

[figure not shown]
3.1 Primary

- To compare the effect of prophylactic oral or enteric apixaban versus no systemic anticoagulant during ~28 days of induction chemotherapy including asparaginase on the composite endpoint of adjudicated non-fatal deep vein thromboses (DVT, including symptomatic and asymptomatic), pulmonary embolism (PE), and CVST; and VTE-related-death.
- To assess the effect of prophylactic oral or enteric apixaban versus no systemic anticoagulant during ~28 days of induction chemotherapy including asparaginase on adjudicated major bleeding events.

3.2 Secondary

- To assess the effect of prophylactic oral or enteric apixaban versus no systemic anticoagulant during ~28 days of induction chemotherapy including asparaginase on single adjudicated endpoints of non-fatal DVT (including symptomatic and asymptomatic), PE, and CVST; and VTE-related-death.
- To assess the effect of prophylactic oral or enteric apixaban versus no systemic anticoagulant during ~28 days of induction chemotherapy including asparaginase on the composite endpoint of adjudicated major and clinically relevant non-major bleeding (CRNMB) events.

4 ENDPOINTS

4.1 Primary Endpoints

Efficacy:

The primary efficacy endpoint is a composite of adjudicated non-fatal DVT (including asymptomatic and symptomatic), PE, and CVST and VTE-related-death objectively confirmed by independent adjudication. All components of the primary efficacy endpoint will be adjudicated by a blinded, independent adjudication committee.

Safety:

The primary safety endpoint will be adjudicated major bleeding which is defined as bleeding that satisfies one or more of the following criteria: (i) fatal bleeding; (ii) clinically overt bleeding associated with a decrease in hemoglobin of at least 20g/L (ie, 2g/dL) in a 24-hour period; (iii) bleeding that is retroperitoneal, pulmonary, intracranial, or otherwise involves the CNS; and/or (iv) bleeding that requires surgical intervention in an operating suite, including interventional radiology. Of note, the major bleeding will not be considered as part of the primary endpoint for the purpose of the European application, but will be assessed as part of the safety profile of apixaban.

Prophylactic transfusions without overt bleeding and without a decrease in hemoglobin of at least 20 g/L (i.e., 2 g/dL) in a 24-hour period are not considered bleeding events.

All bleeding events will be adjudicated by a blinded, independent adjudication committee as major bleeding, CRNM bleeding, or minor bleeding. These endpoints are consistent with those recommended by the International Society on Thrombosis and Haemostasis for pediatric clinical trials in venous thromboembolism.

4.2 Secondary Endpoints

Efficacy:

- a) Non-fatal asymptomatic DVT
- b) Non-fatal symptomatic DVT
- c) Non-fatal PE

- d) CVST
- e) VTE-related-death

Safety

[figure not shown]
- a) Composite of major and CRNM bleeding

[figure not shown]
CRNM bleeding is defined as bleeding that satisfies one or both of the following:

- 1) overt bleeding for which blood product is administered and not directly attributable to the subject's underlying medical condition and
- 2) bleeding that requires medical or surgical intervention to restore hemostasis, other than in an operating room

Pharmacokinetics and Anti-FXa Activity

- a) Apixaban pharmacokinetics using a population pharmacokinetic (PPK) approach
- b) Anti-FXa activity

4.4 Pharmacokinetics

PPK, PK-AXA relationship, and exposure-response (safety/efficacy) relationship will be assessed as data permit.

5 SAMPLE SIZE AND POWER

With a total of approximately 500 randomized subjects allocated with 1:1 ratio to the systemic thromboprophylaxis with apixaban or no systemic anticoagulant prophylaxis (control) group, there is more than 80% power to demonstrate superiority at a one-sided 0.025 level, assuming the true event rates of primary endpoint (composite of non-fatal asymptomatic and symptomatic DVT, pulmonary embolism (PE), and CVST; and VTE-related-death) are 17% and 8.5% in the control and the apixaban groups, respectively. Sample size estimation is based on Pearson's chi-square test.

Additionally, there is more than 80% power to demonstrate superiority at a one-sided 0.025 level, assuming the true event rates are 20% and 10% in the control and the apixaban groups, respectively with analyses that assume that 20% of the subjects will be excluded from the primary analysis due to either early dropout without end-of-treatment imaging evaluation or non-evaluable end-of-treatment imaging measurement in the calculation.

Randomization will be stratified by age groups as <10 years or ≥ 10 to <18 years, to reflect the major peaks of disease prevalence and risk stratification criteria for acute lymphoblastic leukemia (ALL) in children.

6 STUDY PERIODS, TREATMENT REGIMENS AND POPULATIONS FOR ANALYSES

6.1 Study Periods

The term “**Intended Treatment Period**” will refer to the period from day of randomization through Day 29 visit. This period will be the basis for the summaries of efficacy.

The term “**Treatment Period**” will refer to the period from the day of randomization through the end of treatment Day 29 visit or early discontinuation from study (whichever comes first).

The term “**On-treatment Period**” will refer to the period from the day of first dose through the last dose of study medication. This period will be the basis for the summaries of apixaban safety only, because only the apixaban arm will have dose information.

The term “**Follow-up Period**” will refer to the period starting the day after the Day 29 visit or early discontinuation to Day 35 days visit.

6.2 Treatment Regimens

Subjects will be randomly assigned by the IVRS to either apixaban twice daily (see Table 2.1-1) or standard care (control) group. Apixaban will be provided by Bristol-Myers Squibb and is described in Table 6.2-1.

Product Description and Dosage Form	Potency	Label Type	Packaging/Appearance	Storage Conditions (per label)
BMS-562247-01 Film Coated Tablet	2.5 mg	Open label	Bottle	Refer to the label on container
BMS-562247-01 Oral Solution (In study CV185-155 not to be used in children < 5 years of age)	0.4 mg/mL	Open label	Bottle	Refer to the label on container
BMS-562247-01 Film Coated Tablet	0.5 mg	Open label	Bottles in kit	Refer to the label on container

Specific information regarding study drug preparation and administration will be provided to the site.

6.3 Populations for Analyses

The following population will be used for the analyses.

Enrolled Population

The Enrolled Subjects population consists of all subjects who signed informed consent.

Randomized /Intent-To-Treat (ITT) Population

The Randomized/Intent-to-treat (ITT) population consists of all subjects who were randomized to a treatment, regardless of whether they received study drug or not. Except as noted otherwise, the ITT Population will be used for evaluation of efficacy.

Modified Intent-To-Treat (mITT) Population

The mITT population includes randomized subjects who have either an adjudicated event making up the primary efficacy endpoint or evaluable end of study imaging evaluations, including ultrasound and echocardiogram

Evaluable Population

The Evaluable population will include the Randomized/ITT population, except those subjects with relevant protocol deviations expected to affect the primary efficacy endpoint.

The relevant protocol deviations, used to determine exclusions, are listed in [Section 7.2](#).

Safety Population

The safety population for safety endpoints includes all randomized subjects, since there is no intervention on top of standard of care in the control arm. Additional analyses will be performed for subjects treated with apixaban.

Pharmacokinetic (PK) Population

The analysis population for pharmacokinetic assessments will include subjects who have received at least one dose of apixaban and have a pharmacokinetic sample collected.

Pharmacodynamics (PD) Population

The analysis population for anti-FXa assessments will include subjects who have received at least one dose of apixaban and have anti-FXa samples collected.

Subgroup Populations

Table 6.3-1 shows the subpopulations of interest for analyses of efficacy and bleeding.

Table 6.3-1: Subgroups of Interest for Efficacy and Bleeding Assessments

Grouping Variable	Subgroups
Geographic region	North America Europe Latin America Asia/Pacific
Age (stratification variable)	< 10 years old ≥10 to < 18 years old
Age category	Young Children 1 year to <2 years Young Children 2 years to 6 years Children 6 years to <12 years Adolescents 12 years to <18 years
Ethnicity	Hispanic/Latino

Table 6.3-1: Subgroups of Interest for Efficacy and Bleeding Assessments

Grouping Variable	Subgroups
	Not Hispanic/Latino
Gender	Male Female
Race	White Black / African American Asian Other
Weight	< 35 kg ≥35 kg
Obesity	Non-obese (less than the 95th percentile of age- and sex-specific BMI)* Obese (Equal to or greater than the 95th percentile of age- and sex-specific BMI)*
ALL risk	Standard risk (WBC count less than 50,000/ μ L and age 1 to younger than 10 years) High risk (WBC count 50,000/ μ L or greater and/or age 10 years or older)
Central line	Peripherally inserted central catheters (PICC) lines All tunneled lines (including totally implanted devices/ports) All others (“non-tunneled line” and “other” from below, which will likely number 0 or at least a very small number of patients)

* The definition that is based on Central for Disease Control and Prevention criteria

7 STATISTICAL ANALYSES

SAS® version 9 or higher will be used for statistical analyses, tabulations and graphical presentations.

7.1 General Methods

Descriptive summaries will be presented for continuous variables using number of subjects (N), mean, standard deviation (SD), median, minimum and maximum. Descriptive summaries for categorical variables will utilize counts and percentages.

Adverse events will be coded according to the most recent Medical Dictionary for Regulatory Activities (MedDRA) version. Adverse events will be summarized according to the MedDRA coded Preferred Terms (PT) by System Organ Class (SOC). Previous and concomitant medications will be coded using the WHO Drug Dictionary version.

Unless otherwise specified, baseline is defined as the last non-missing result with a collection date-time prior to the date-time of the randomization.

Testing for Treatment by Subpopulation Interaction

For efficacy subgroup analyses, Wald's chi-square test will be used to test whether treatment has a statistically significantly different ($p < 0.1$) effect on the event rate of an endpoint across subgroups (e.g. male, female) based on a logistic model with terms for treatment, stratification variable age, subpopulation, and treatment by subpopulation interaction.

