7.5.4 Subgroup Analysis

Rates for the primary efficacy endpoint will also be summarized by treatment group and subgroups listed in Table [Table 6.3-1](#). Ninety-five percent (95%) CIs for the ratio of event rates will be computed based on Mantel-Haenszel’s method stratified by the stratification factor(s) as applicable

The analyses will be performed using events occurring during the Intended Treatment Period and for the Primary endpoint (when summarizing the primary efficacy endpoint). If the value of the

grouping variable cannot be determined for a subject, the subject will be excluded from the corresponding subgroup analysis. For each subpopulation analysis, if, in any treatment group, the number of subjects is ≤ 10 for a subgroup, then the grouping variable will not be included in the test of treatment by subpopulation interaction.

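### The subgroup interaction test has no rule for a subgroup with no events in one arm; for a two-level factor the planned Wald p-value is then about 1, whatever the difference

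*SAP*

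**What the plan says.** SAP 7.1 (General Methods) states that, for efficacy subgroups, Wald's "chi-square test will be used to test whether treatment has a statistically significantly different" effect on an endpoint's event rate across subgroups, with p < 0.1 as the threshold. The model is logistic, with terms for treatment, the age stratum, the subgroup factor and their interaction (treatment by subgroup). No estimation method is named and there is no exact, penalised or likelihood-ratio fallback, so maximum likelihood is the natural reading.

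SAP 7.5.4 gives the one safeguard. If any treatment group has 10 or fewer subjects in a subgroup, "then the grouping variable will not be included in the test of treatment by subpopulation interaction". The same section reports event rates by arm and subgroup, with confidence intervals for their ratio.

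Table 6.3-1 lists ten grouping variables. Region, age category and race have four levels each and central line has three. The other six (age stratum, ethnicity, gender, weight, obesity, ALL risk) have two.

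**The concern.** The endpoint is infrequent: in SAP 5 the planning rates "are 17% and 8.5% in the control and the apixaban groups, respectively". A small subgroup can therefore pass the 10-subject rule and still have no events in one arm. The maximum-likelihood interaction coefficient then has no finite value. Its standard error grows faster than the estimate, and the Wald statistic collapses towards zero.

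What is at stake is how the subgroup table reads. An interaction p-value near 1 is normally taken as support for a consistent effect. Here it would reflect only that the test had failed, and it would look the same whether all the events in that subgroup were in the control arm or all in the apixaban arm.

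**Working it through.** **The plan's own figures.** SAP 5 gives no figure for the interaction test. Its power statement supplies the arm sizes and rates used below: "With a total of approximately 500 randomized subjects allocated with 1:1 ratio", "there is more than 80% power to demonstrate superiority at a one-sided 0.025 level". With the pooled Pearson chi-square, 250 per arm and 17% v 8.5%, power is 81.5%. With 20% v 10% and 20% excluded (500 × 0.8 = 400, so 200 per arm), power is 80.2%. Both reproduce.

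**How often a cell is empty.** For a level with n children per arm at the planned rates, P(no events in at least one arm) = 1 − (1 − 0.915^n)(1 − 0.83^n).

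| n per arm | apixaban empty | control empty | either |
|---|---|---|---|
| 11 | 37.6% | 12.9% | 46% |
| 20 | 16.9% | 2.4% | 19% |
| 25 | 10.9% | 0.9% | 12% |
| 30 | 7.0% | 0.4% | 7% |
| 50 | 1.2% | 0.01% | 1.2% |
| 100 | 0.01% | about 0 | 0.01% |

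The sizes are assumptions, because the documents give none.

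**What the test returns.** Wald = (estimate/SE)². The Firth test maximises l*(β) = l(β) + ½ log|I(β)|. Its penalised likelihood-ratio statistic is 2[l*(full) − l*(interaction fixed at 0)], referred to chi-square. Tables are apixaban v control, 250 per arm. The 25-per-arm rows omit the age term; the 60-per-arm rows include it.

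| Level A | Remainder | Wald p | Comparison |
|---|---|---|---|
| 0/25 v 8/25 | 21/225 v 30/225 | > 0.99 | Firth LR 0.011 |
| 8/25 v 0/25 | 21/225 v 30/225 | > 0.99 | Firth LR 0.0006 |
| 1/25 v 8/25 | 21/225 v 30/225 | 0.078 | Firth LR 0.059 |
| 0/60 v 20/60 | 21/190 v 22/190 | 0.99 (estimate −17.5, SE 1158) | ordinary LR < 0.0001 |
| 1/60 v 20/60 | 20/190 v 22/190 | 0.003 | ordinary LR 0.00005 |

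The Wald value depends on where iteration stops. In the 0/60 table, refitted without the age term, it was 0.51 when cut at 8 iterations and 0.97 to 0.999 at 15 or more.

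**More than two levels.** With 3/100 v 20/100, 18/100 v 10/100 and 0/50 v 12/50, the joint Wald p is 0.0014, carried by the first two levels. With 10/100 v 15/100, 11/100 v 16/100 and 0/50 v 12/50, where the first two agree, Wald p is 0.999 and the ordinary likelihood ratio gives 0.003.

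**Operating characteristics** (two-level factor, 1500 simulated trials per setting, age term omitted; ranges are two independent runs). Under interaction, level A is 2% v 30% and the rest 12% v 16%.

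| Setting, level A size | Wald, p < 0.1 | Firth LR | Ordinary LR |
|---|---|---|---|
| Interaction, 25 per arm | 20–21% | 76–77% | – |
| Interaction, 40 per arm | 47–48% | 93% | – |
| No interaction, 25 per arm | 5.6–6.4% | 8.7–9.4% | 14.5–14.7% |

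In a separate set of simulations with the age term included, no trial with an empty cell reached p < 0.1; the lowest Wald p among them was 0.983.

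**The case against.** A reader might infer that the test gives p near 1 whenever any subgroup has an empty cell, or that it is blind to the largest subgroup differences in general. Neither holds. The joint test on a three- or four-level factor can be significant from its other levels, as shown. One event in the sparse arm usually restores detection (1/25 v 8/25 is flagged at 0.078). Nor is every empty cell a hidden signal: 0/25 v 5/25 against 21/225 v 38/225 gives a Firth likelihood-ratio p of 0.117, so the better test does not flag it either.

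The levels most obviously at risk of being small (ages 1 to under 2, some races and regions) all belong to multi-level factors, whereas the total failure occurs with two levels. Line type is a weak example: Table 6.3-1 expects its residual category to be almost empty, in which case SAP 7.5.4 removes the whole variable from the test. This limits the scope but does not rescue the Wald test. In a small four-level simulation (300 trials, 25 per arm in one level, assumed rates) it detected 12% of interactions and the Firth test 55%.

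It is also tempting to say that the plan would routinely conceal harm. With 30% v 10% in a 25-per-arm level and 8% v 17% elsewhere (600 trials), Wald detected 78% and Firth 86%, because a cell was empty in only 8% of trials. Harm is masked only when the control cell is empty.

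Finally, the rates and ratio intervals planned in SAP 7.5.4 would put 0% v 32% in front of the reader. That softens the consequence. It does not make the p-value beside those rates meaningful.

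**Conclusion.** The gap is real and narrow. For a two-level factor with no events in one arm of one level, the planned test cannot reject, and the 10-subject rule does not prevent this. For factors with more levels it loses the empty level's contribution. At the planned rates this matters for levels of roughly 11 to 30 per arm (46% down to 7% chance of an empty cell) and hardly at all from 50 per arm upwards, unless the true rate in that level is well below plan.

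The conclusion rests on maximum likelihood being the intended fit, on assumed subgroup sizes, and on the overall planning rates applying within the level. It concerns a supportive analysis: the stratified Mantel-Haenszel test of the primary endpoint, its alpha and its power are untouched. It should be corrected, but it does not threaten the trial's main conclusion.

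**What to change.** In SAP 7.1, replace the Wald test with the penalised likelihood-ratio test from Firth logistic regression, keeping the same model terms and the p < 0.1 flag. Name the likelihood-ratio form explicitly: a Wald test from the same Firth fit gives 0.069 in the 0/25 v 8/25 example, against 0.011. Do not substitute the ordinary likelihood-ratio test, which rejects too often in small levels (about 14.5% at a nominal 10%). Show event counts per arm beside each interaction p-value.

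The cost is one sentence in the SAP and slightly more programming. In small levels the false-positive rate rises from about 6% to about 9%, which is closer to the nominal 10%. A score or exact test, or a minimum number of events per cell, would also close the gap. Whichever is chosen should be fixed before outcome data by arm are seen, so that it is not improvised when an empty cell appears.
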